7.17 Participant Retention

The target retention rate will be 90% per annum. During the informed consent process the participant will be informed of the planned retention procedures. This is to ensure participant awareness of all the efforts that will be undertaken to contact them in the event that they miss a scheduled study visit throughout the participant's Involvement in the study (up to 2 years for those who enroll early in pregnancy). Study participants will be informed that staff will attempt to make telephonic contact with them for missed visits or for unscheduled visits if the need arises, failing which home visits will be made. The Protocol Team will track retention rates. Once a participant is enrolled in the study, study staff will make every reasonable effort to ensure adequate locator information is available for follow-up tracking. A missed visit in either arm will prompt a single telephonic reminder, where the participant is spoken to directly and reminded of her clinic visit. A home visit will be triggered if a second clinic visit is missed. A home visit will be considered complete when the participant is met in person. A maximum of 3 attempts will be made to complete a home visit. Retention efforts will be conducted by the same team for both arms.

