Based on current data (maternal adverse events, maternal and infant bone mineral content depletion), all other adverse birth outcomes and maternal and infant adverse events can be housed within this sample size and will have smaller D as the relative prevalence decreases toward 0 i.e. narrower equivalence zones. Assuming a loss to follow-up of 5%, we would need 442 women in each group (884 in both arms combined) for the two year time frame of the study.

Outcome	n/N	Prevalence	Required sample size in each group for proposed equivalence trial	Total required sample size for proposed equivalence trial
Pre-term	1096/5916	18.5%	421	842
LBW	651/5916	11.0%	274	548
Small for GA	429/5916	7.3%	189	378
VLBW	141/5916	2.4%	64	128
Stillbirth	130/5916	2.2%	58	116

Main endpoint 1: sample size for safety in pregnancy for birth outcomes Prevalence adverse birth outcomes among HIV-ve (in descending order)

Based on a non-inferiority trial design: A sample size of 421 in the treatment group and 421 in the control group (i.e. 842 in total) achieves 80% power to detect a non-inferiority margin difference between the group proportions of 0.075 or 7.5%. The reference group proportion (pre-term delivery birth outcome) is 0.185 or 18.5%. The treatment group proportion is assumed to be 0.26 or 26% under the null hypothesis of inferiority. The power was computed for the case when the actual treatment group proportion is 0.185 or 18.5%. The test statistic used is the two-sided Z test (unpooled). The significance level of the test was targeted at two-sided 0.05 or 5%.

Secondary Endpoint

PASS 12 sample size software (Hintze, J. (2013). PASS 12. NCSS, LLC. Kaysville, Utah, USA. www.ncss.com) was to calculate this sample size. In order to show a 50% reduction in HIV infections, with significance level of 0.05 or 5% and 80% power, we would need to observe 66 HIV infections in total (44 in control arm [cumulative incidence of 12.72%] and 22 in the intervention arm [cumulative incidence of 6.36%]). This assumes an HIV incidence of 3 per 100 person years during the 6 months of pregnancy and 6 per 100 person years during the 18 months of breastfeeding [9]. Based on these assumptions, we would require 334 subjects in group or 668 in total. Assuming a loss to follow-up of 10%, we would need to increase this to 346 women in each group (692 in both arms combined) for the two year time frame of the study.

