The primary objective is to compare the frequency and seriousness of adverse events in women receiving tenofovir/emtricitabine in pregnancy and their newborn as opposed to women not receiving tenofovir/emtricitabine during pregnancy and their newborn. The number of adverse events experienced during pregnancy and post-delivery will be summarized for each of the study arms. This will also be stratified by seriousness of the adverse event. The number of adverse events will be compared between the study arms using Fisher's Exact test. Furthermore we will use the most widely used approach to test equivalence, namely the two one-sided test (TOST) procedure (Schuirmann DJ. A comparison of the two one-sided tests procedure and the power approach for assessing equivalence of average bioavailability. J Pharmacokin Biopharm. 1987;15:657–680. doi: 10.1007/BF01068419). Furthermore we will also employ a hierarchical or random effects modeling approach for a non-inferiority analysis for the primary endpoints.

A secondary objective is to compare the number of incident HIV infections in women during pregnancy alone and thereafter during breastfeeding. The analysis will be stratified by levels of PrEP adherence, partner involvement, condom usage and relationship dynamics. The cumulative incidence and associated 95% confidence intervals will be calculated for each study arm. The number of incident events will be compared for statistical difference between the study arms using Fisher's Exact test.

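### HIV infections are compared as raw counts by Fisher's exact test, so the result depends on how follow-up is lost in each arm; a time-to-event comparison would remove this and avoid a small power cost from Fisher's conservatism

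*Combined protocol and SAP*

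**What the plan says.** For the secondary HIV objective, section 10.4 says: "The number of incident events will be compared for statistical difference between the study arms", and names Fisher's exact test for this. Just before that it says: "The cumulative incidence and associated 95% confidence intervals will be calculated for each study arm". It does not say how cumulative incidence is estimated, how a woman lost before 18 months is counted, or when she is censored. The same section applies intention-to-treat to everyone randomised, limits itself to the primary safety endpoint, and leaves full detail to a SAP still to be written. It names this HIV test nonetheless.

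Section 10.3 plans the endpoint from 3 infections per 100 person-years over 6 months of pregnancy and 6 per 100 over 18 months of breastfeeding. It aims for a halving of infections "with significance level of 0.05 or 5% and 80% power", and says "we would need to observe 66 HIV infections in total", with cumulative incidences of 12.72% and 6.36%, 334 women per group, and 10% loss. Section 7.17 adds: "The target retention rate will be 90% per annum". The planned enrolment of 442 per arm comes from the preterm-delivery calculation.

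Infection times will be available. Section 7.20 has a rapid test at every visit, section 7.9 sets visits about every four weeks, and section 7.14 has earlier samples tested by PCR to date the infection. Section 10.2, however, defines the HIV outcome by NAT at 3-monthly visits.

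**The concern.** A count of women seen to seroconvert depends on two things: the rate of infection and how long each arm was watched. Fisher's test on counts cannot separate them. If one arm loses more women, it shows fewer infections for that reason alone. The trial is open label (section 10.1), and only Arm A receives study drug before breastfeeding ends, so unequal loss is possible.

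Time at risk also varies without any loss. Section 3.1 gives a mean gestation of 28 weeks at first antenatal visit, with 48% registering before 20 weeks, and breastfeeding ends at different times. Section 10.4 wants infections looked at separately in pregnancy and in breastfeeding, and counts alone do not measure incidence in either period.

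At stake is the trial's only between-arm comparison of HIV infection. It is a secondary objective, so the matter is worth correcting but does not threaten the primary safety aim.

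**Working it through.** **1. The plan's own figures (section 10.3).**

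- Events for a log-rank test at hazard ratio 0.5, two-sided 5%, 80% power: 4 × (1.96 + 0.8416)² / (ln 0.5)² = 65.3, rounded up to 66. This matches.
- Women per group, pooled two-proportion formula at 12.72% v 6.36% (mean 9.54%): [1.96 × √(2 × 0.0954 × 0.9046) + 0.8416 × √(0.1272 × 0.8728 + 0.0636 × 0.9364)]² / 0.0636² = 334. This matches too.

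So the sizing mixes a log-rank event count with a two-proportion sample size, and neither is Fisher's test. On 12.72% v 6.36% with 334 per group, Fisher's power is 77.0% by exact enumeration.

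- The stated rates give a lower risk: 0.03 × 0.5 + 0.06 × 1.5 = 0.105, and 1 − exp(−0.105) = 10.0% (5.1% if halved), not 12.72%. Results below use the stated rates unless noted.

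**2. Size of the bias with no true effect.** Assume exponential loss unrelated to HIV risk, at rate λ = −ln(1 − loss)/2 per year. If lost women are counted as uninfected, the expected proportion seen to seroconvert is

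0.03/(0.03 + λ) × [1 − exp(−0.5(0.03 + λ))] + exp(−0.5(0.03 + λ)) × 0.06/(0.06 + λ) × [1 − exp(−1.5(0.06 + λ))].

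| Loss over 2 years | λ | Proportion seen |
|---|---|---|
| 10% | 0.0527 | 0.0941 |
| 19% (1 − 0.9²) | 0.1054 | 0.0890 |
| 28% (assumed) | 0.1643 | 0.0836 |

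Ratios: 10% v 19%, 0.0890/0.0941 = 0.95, or 1.06 reversed. 10% v 28%, 0.0836/0.0941 = 0.89, or 1.13 reversed. The true ratio is 1.

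If women lost without infection were dropped instead, the bias changes direction. Completing uninfected takes probability 0.9003 × 0.90 = 0.8103 or 0.9003 × 0.72 = 0.6482. The proportions become 0.0941/(0.0941 + 0.8103) = 0.104 and 0.0836/(0.0836 + 0.6482) = 0.114, a ratio of 1.10 where the first rule gave 0.89.

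**3. Simulation, 442 per arm, 4,000 trials per setting** (Monte Carlo standard error about 0.7 point at 75%, 0.3 point at 5%), lost women counted as uninfected.

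No true effect, unequal loss in either direction:

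| Loss | Raw ratio | Fisher error | Person-year ratio | Log-rank error |
|---|---|---|---|---|
| 10% v 19% | 0.94–1.06 | about 4–5% | 0.99–1.02 | about 5% |
| 10% v 28% | 0.89–1.13 | about 7% | 0.99–1.02 | about 5% |

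True hazard ratio 0.5, heavier loss in the control arm: at 10% v 19%, Fisher 62% and log-rank 75%; at 10% v 28%, 51% and 74%. With heavier loss in the PrEP arm the error runs the other way: at 25% PrEP v 10% control, Fisher rejects in 81% of trials against 74% for log-rank, and the excess is bias.

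**4. Equal loss, true hazard ratio 0.5.** A plain chi-square test on the same counts shows where the power goes:

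| Loss in both arms | Fisher | Chi-square | Log-rank |
|---|---|---|---|
| 0% | 75% | 79% | 79% |
| 10% | 71% | 76% | 76% |
| 19% | 70% | 75% | 75% |

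Chi-square ignores timing exactly as Fisher does, yet equals log-rank. The gap is therefore Fisher's conservatism, whose actual error with no loss is 3.7%. With rates scaled to reach 12.72%, at 19% loss the figures are about 79% (Fisher) and 83% (log-rank).

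**The case against.** The strongest reply is that the bias rests on an assumed imbalance. The documents give no loss by arm. Section 7.17 uses the same retention team for both arms, visits are common to both, and travel is compensated. At 10% v 19%, Fisher's error stays at or below nominal because its conservatism absorbs the bias. That stands: the harm under the null is small unless the gap is wide. The loss of power at 10% v 19% does remain.

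Second, section 10.4 leaves detail to a later SAP and already plans cumulative incidence, which could be a Kaplan-Meier estimate. Also fair, but no estimator is named and the test itself is on counts.

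A reader might draw four stronger conclusions, none of which the documents support:

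- That ignoring timing costs power. With equal loss, the chi-square comparison shows no measurable cost.
- That a woman lost at 2 months is to be scored as uninfected for the full period. Including everyone randomised makes this the plain reading, but no rule is written.
- That the 66 events show a log-rank test was intended. The 334 per group comes from a two-proportion formula.
- That power in the low 70s is the fault of the test. Most of the shortfall comes from the gap between the stated rates (10.0%) and the stated 12.72%, a separate inconsistency.

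Finally, a log-rank test is no cure for loss that is itself related to HIV risk.

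**Conclusion.** The point holds in a limited form. The named comparison leaves the HIV result exposed to unequal follow-up, and the dates needed to avoid this are already being collected. The bias is conditional: small under the null at 10% v 19% loss, and material at 10% v 28%. A true halving becomes clearly harder to detect in both cases when the control arm loses more women. With equal loss the cost is about 4 to 5 points of power and is due to Fisher's conservatism alone.

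These figures assume 442 per arm, the stated incidence rates, exponential loss unrelated to HIV risk, and lost women counted as uninfected. The 28% loss and any difference between arms are assumptions for illustration, not figures from the documents.

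**What to change.** In the SAP, before analysis begins:

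- Replace Fisher's test with a log-rank comparison of time from randomisation to first HIV-positive sample, censored at the last negative test.
- Name Kaplan-Meier as the estimator of the cumulative incidence already planned, with 95% CI by arm at delivery and at 18 months.
- Report infections per 100 person-years with exact CI, separately for pregnancy and for breastfeeding.
- Give any Cox hazard ratio by period, or only up to breastfeeding cessation. Both arms may choose PrEP after that point (sections 6.2 and 7.11), so one constant ratio over 18 months is doubtful.
- Add a sensitivity analysis for loss related to HIV risk.
- Reconcile the 3-monthly NAT outcome in section 10.2 with testing at every visit in sections 7.9 and 7.20.

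The cost is SAP wording and a little more analysis. No new data are needed, since test dates and stored samples are already in the schedule. The main comparison will still assume that loss is unrelated to HIV risk, which is why the sensitivity analysis belongs with it.

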11. REGULATORY AND ETHICAL ISSUES

11.1 Regulatory Compliance

The study complies with the principles of the Declaration of Helsinki (2008). It will be conducted in compliance with approval from the South African Medicines Control Council and the University of KwaZulu-Natal Biomedical Research Ethics Committee.

11.2 Participant Confidentiality

All laboratory specimens, evaluation forms, reports, and other records that are transferred or transmitted off-site for processing will be identified only by a coded number to maintain subject confidentiality. All records will be kept in a secured area with access limited to authorized personnel only. All computer entry and networking programs will be performed with coded numbers only. Clinical information will not be released without written permission of the participant.

11.3 Ethical Considerations

Pre-exposure antiretroviral prophylaxis comprising a daily dose of Truvada (Tenofovir/Emtricitabine) is a proven prevention strategy for same sex couples and discordant couples and now internationally recommended for individuals at substantial risk. The benefit of PrEP in high risk population groups significantly outweigh the potential threat of adverse events. The high risk population groups are MSMs, men in incarceration, commercial sex workers and adolescent girls and young women. Additional options for PrEP in young women through long acting antiretroviral (Dapivirine) prophylaxis in vaginal rings are also possible, but preclude use in pregnancy.

Truvada (the antiretroviral drug of choice for PrEP) is classified as a FDA pregnancy Category B antiretroviral. Pregnancy and lactation are distinct contraindications to initiate PrEP because of the limited evidence of its (Truvada) adverse effects on the child. Despite this classification, Truvada has been endorsed by the WHO to be used as part of a treatment combination in HIV infected pregnant women and to reduce motherto-child transmission of HIV. Arguably, the benefits outweigh the potential risk of adverse events (minimal) in this HIV infected population. On the other hand, in all HIV uninfected pregnant women in general, the benefit may be minimal.

Because younger pregnant and lactating women are disproportionately at risk for HIV infection, a targeted intervention approach for women in this particular group would be ethically acceptable to demonstrate the safety of the current standard approach to preventing sexually transmitted infections strengthened by the use of antiretroviral prophylaxis -Truvada (TDF/FTC). The Intervention Package would therefore include a daily dose of Truvada (TDF/FTC), risk reduction counselling, STI screening and treatment, inviting the sexual partner to receive HCT and referral for treatment and support if he tests HIV positive and condom promotion. The Control Group of young pregnant women will receive the above package minus the antiretroviral prophylaxis -Truvada (TDF/FTC).

Women participating in the PrEP study will receive compensation for travel costs incurred at each scheduled study visit.

HIV Prevention Pregnancy Post-delivery Version 1.0

Appendix 2 HIV RISK ASSESSMENT TOOL

PID			Initials:
1. How o	old are you?		
	<25	1	
	> 25	0	

2. Are you married or living with your partner?

No	1	
Yes	0	

3. How old is your current partner?

> 25	1	
<25	0	

4. What is the HIV status of your partner?

Positive	1	
Unknown	1	
Negative	0	

5. Does your partner have other girlfriends?

Yes	1
l do not know	1
No	0

6. Does your partner provide you with financial support?

Yes	1	
No	0	

7. Have you had any alcohol in the last 3 months?

Yes	1	
No	0	

Final Score _____

High Risk	> 3	
Moderate or Low Risk	<3	

Risk Assessment Tool modified from : An Empiric **HIV** Risk Scoring Tool to Predict **HIV**-1 Acquisition in African Women. Balkus JE, Brown E, Palanee T, et al. J Acquir Immune Defic Syndr. 2016 Feb 25. [Epub ahead of print] .

APPENDIX 5 SCHEDULE OF EVENTS FOR MOTHER

		ANTENATAL			LABOUR AND DELIVERY	POSTNATAL					
	SCREENING 1 ^{sr} ANTENATAL VISIT	2 [№] ANTENATAL ENROLMENT 14W	3 RD ANTENATAL 2 WEEKS	SUBSEQUENT 4 WEEKLY ANTENATAL	<72 HOURS POST DELIVERY	2 WEEKS	6 WEEKS	10 WEEKS	14 WEEKS	SUBSEQUENT 4 WEEKLY POSTNATAL	74 WEEKS/STUDY EXIT
Study Informed Consent	Х	Х									
Storage Informed Consent		х									
Documented HIV test result	Х	~									
HIV Risk Assessment	Х										
Medical History	Х										
Hx, Signs/Sx of STIs	Х		Х	Х	Х	Х	Х	Х	Х	Х	Х
Pregnancy Ultrasound	Х										
Obstetric Assessments	Х	Х	Х	Х							
DXA Scan Hip and Lumbar Spine							Х			X*	Х
Physical Exam	Х	Х	Х	Х	Х	Х	Х	Х	Х	Х	Х
Randomisation		Х									
Sexual Behaviour Questionnaire	Х	Х	Х	Х	Х	Х	Х	Х	Х	Х	Х
Drug Adherence Interview			Х	Х	Х	Х	Х	Х	Х	Х	Х
Condom Usage Interview		Х	Х	Х	Х	Х	Х	Х	Х	Х	Х
Risk Reduction Counselling		Х	Х	Х	Х	Х	Х	Х	Х	Х	Х
Laboratory Investigations											
RPR Test	2ml								2mL		2mL
HIV Rapid Test (finger prick)	Х	Х	Х	Х	Х	Х	Х	Х	Х	Х	Х
Hep B Surface Antigen	2ml						2mL				2ml
ALT/AST/Phosporous		2ml		2mlª				2ml		2mlª	
CBC	2ml		2ml	2mlª	2mL				2mL	2mlª	
Serum Creatinine	2mL		2mL	2mL		2mL		2mL	2mL	2mL	2mL
Stored EDTA Plasma, DBS /cell pellets		10mL	10mL	10mL	10mL	10mL	10mL	10mL	10mL	10mL	10mL
Stored Breast Milk (during BF only)						10mL	10mL	10mL	10mL	10mL	10mL
Cervical Vaginal Swabs		Х	Х	Х			Х	Х	Х	Х	Х
TOTAL BLOOD VOLUME	8ml	12ml	14ml	16ml	12ml	12ml	12ml	14ml	14ml	16ml	12ml

* DXA scan at 6 and 12 months

APPENDIX 6

SCHEDULE OF EVENTS FOR HIV UNEXPOSED INFANTS

	BIRTH	6 WEEKS	26 WEEKS	50 WEEKS	72 WEEK/STUDY EXIT VISIT
Physical Exam	Х	Х	Х	Х	Х
Growth Parameters and neurodevelopmental milestones	Х	X	Х	Х	X
DXA Scan Lumbar Spine and Whole Body		Х	Х	Х	X
Laboratory Investigations					
CBC	2mL	2ml	2mL	2mL	2mL
Serum Creatinine	2mL	2ml	2mL	2mL	2mL
Stored DBS	Х	Х	Х	Х	Х
TOTAL BLOOD VOLUME	4ml	4ml	4ml	4ml	4ml
